	
identified area and removal of delivery system in the absence of in-hospital MAEs.
 
 • Clinical Success defined as Limb ischemia improvement by Rutherford-Becker (improvement in scale by ≥ 1) through follow-up. • Limb ischemia by Rutherford-Becker Classification through follow-up. • Primary Patency through follow-up. • Primary assisted patency defined as revascularization of non-occlusive (<99%) stenosis within the stent graft or immediately above or below the treated arterial segment with less than 50% residual stenosis through follow-up. • Secondary patency defined as: revascularization of occlusion (100%) within the stent graft or immediately above or below the treated arterial segment with less than 50% residual stenosis through follow-up. • Ankle-Brachial Index (ABI) through follow-up. • Target vessel revascularization (TVR) through follow-up. • Number of any type of index limb amputations through follow-up. • Number of vessel run-offs through follow-up.
DSMB	
A Data Safety Monitoring Board (DSMB) consisting of non-Investigator experts, will review safety data from the study and establish stopping rules for early termination of the trial. The DSMB will make recommendations based upon the safety analysis of adverse events, protocol deviations, and device failures. The DSMB will function in accordance with SOPs and applicable regulatory guidelines.

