- Primary assisted patency defined as revascularization of non-occlusive (<99%) stenosis within the stent graft or immediately above or below the treated arterial segment with less than 50% residual stenosis through follow-up.
- Secondary patency defined as: revascularization of occlusion (100%) within the stent graft or immediately above or below the treated arterial segment with less than 50% residual stenosis through follow-up.
- Ankle-Brachial Index (ABI) through follow-up.
- Target vessel revascularization (TVR) through follow-up.
- Number of any type of index limb amputations through follow-up.
- Number of vessel run-offs through follow-up.

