11.0 ENDPOINTS AND STATISTICAL ANALYSIS PLAN

11.1 Endpoints Analyses and Reporting of Results

The study objective is to assess the safety and performance of the PQ Bypass System to access, deliver guidewires and implant stent grafts for a percutaneous fem-pop bypass.

The study is a feasibility study with no formal hypothesis testing and therefore no required sample size. Study results will be presented using descriptive statistics. Results from this study will be used to design additional clinical studies.

All subjects will be followed on an intent-to-treat basis. The device performance will be assessed based on a per-protocol analysis of the primary safety and effectiveness endpoints. An Intent-to-treat analysis, along with other secondary analyses, will also be completed and reported.

Demographic, baseline clinical and disease characteristics, procedural results and primary, secondary and all additional endpoints will be summarized using descriptive statistics.

All statistical analyses will be performed using SAS for Windows version 9.1 or higher.

Primary Safety Endpoint Reporting:

Safety assessment is achieved by recording and measuring Major Complication rates/Serious Adverse Event rates associated with the PQ Bypass procedure. The number and percentage 6-month MAE will be presented using descriptive Statistics. Using the Score approximation, the one-sided upper 95% confidence bound will be calculated and presented.

Primary Performance Endpoint Reporting:

Descriptive statistics of the primary performance endpoint which includes total number of patent PQB grafts, number and percentage of patent PQB grafts, and the one-sided 95% CI of the percentage using the Score approximation will be presented. The lower bound of the one-sided 95% CI will be compared to the performance goal of 70% (80% historical control rate – 10% Delta.)

Secondary Endpoint Analysis:

The secondary endpoint of primary assisted and secondary patency will be summarized using Kaplan-Meier survival analysis. Life tables will be created and a Kaplan-Meier survival curve will be presented.

The secondary endpoints of Procedural Success, Clinical Success and Technical

Success will be summarized by providing point estimates, number of subjects, and 95% confidence bounds calculated using the Score approximation.

Demographic, procedural and safety data:

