Methods: From March 2004 to May 2005, 100 limbs in 86 patients with femoropopliteal arterial occlusive disease were identified. Patients had symptoms ranging from claudication to rest pain, with or without tissue loss, and were prospectively randomized for treatment into one of two groups. The limbs were treated percutaneously with angioplasty and one or more self-expanding stent grafts (n=50) or surgically with femoral-to-AK popliteal artery bypass using synthetic Dacron or ePTFE grafts (n=50).

The mean and SD total length of artery stented was 25.6 and 15 cm. Follow-up evaluation with ankle-brachial indices and color flow duplex sonography imaging were performed at 3, 6, 9, and 12 months after treatment.

Patients were monitored for a median of 18 months. No statistical difference was found in the primary patency (P=895) or secondary patency (P=.861) between the two treatment groups. Primary patency at 3, 6, 9, and 12 months of follow-up was 84%, 82%, 75.6%, and 73.5% for the stent graft group and 90%, 81.8%, 79.7%, and 74.2% for the femoral-popliteal surgical group. Thirteen patients in the stent graft group had 14 re-interventions, and 12 re-interventions occurred in the surgical group. This resulted in secondary patency rates of 83.9% for the stent graft group and 83.7% for the surgical group at the 12-month follow-up (**Table 11-2**).

Based on review of the limited literature and the recent long lesion stent graft vs prosthetic surgery randomized study 6-month surgical bypass primary patency rate of 82-85% can be extrapolated.

Table 11-2 Randomized Comparison of Viabahn Stent Graft vs. Prosthetic Surgery

Table IV. Primary patency in femoral-popliteal bypass group and stent graft group

Time post-treatment (months)	N at risk at start of interval	N events during interval*	N censored during interval*	% Free from loss of patency	95% CI
Operative (day 0-30)					
Fem-pop bypass	50	2 (2)	0 (0)	0.960	(0.849, 0.990)
Stent graft	50	2 (2)	0 (0)	0.960	(0.849, 0.990)
3 months (day 31-136)					
Fem-pop bypass	48	3 (5)	1 (1)	0.900	(0.776, 0.957)
Stent graft	48	6 (8)	1 (1)	0.840	(0.705, 0.917)
6 months (day 137-227)					
Fem-pop bypass	44	4 (9)	2 (3)	0.818	(0.680, 0.901)
Stent graft	41	1 (9)	1 (2)	0.820	(0.682, 0.902)
9 months (day 228-319)					
Fem-pop bypass	38	1 (10)	8 (11)	0.797	(0.655, 0.885)
Stent graft	39	3 (12)	1 (3)	0.756	(0.611, 0.854)
12 months (day 320-456)					
Fem-pop bypass	29	2 (12)	8 (19)	0.742	(0.587, 0.846)

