Stent graft	35	1 (13)	7 (10)	0.735	(0.587, 0.837)

CI, Confidence interval.

Log-rank $P = .895$.

*Number in parenthesis represents cumulative events or censored observations through end of interval.

Table V. Secondary patency in femoropopliteal bypass group and stent graft group

Time post-treatment (months)	N at risk at start of interval	N events during interval*	N censored during interval*	% Free from loss of patency	95% CI
Operative (day 0-30)					
Fem-pop bypass	50	2 (2)	0 (0)	0.960	(0.849, 0.990)
Stent graft	50	0 (0)	0 (0)	1.000	(1.000, 1.000)
3 months (day 31-136)					
Fem-pop bypass	48	2 (4)	1 (1)	0.920	(0.801, 0.969)
Stent graft	50	6 (6)	1 (1)	0.880	(0.752, 0.944)
6 months (day 137-227)					
Fem-pop bypass	45	3 (7)	2 (3)	0.859	(0.726, 0.930)
Stent graft	43	1 (7)	1 (2)	0.860	(0.728, 0.930)
9 months (day 228-319)					
Fem-pop bypass	40	1 (8)	8 (11)	0.837	(0.701, 0.915)
Stent graft	41	1 (8)	1 (3)	0.839	(0.703, 0.916)
12 months (day 320-456)					
Fem-pop bypass	31	0 (8)	11 (22)	0.837	(0.701, 0.915)
Stent graft	39	0 (8)	9 (12)	0.839	(0.703, 0.916)

CI, Confidence interval.

Log-rank P value = .861.

*Number in parenthesis represents cumulative events or censored observations through end of interval.

Kedora et al J Vasc Surg 2007;45:10-16

McQuade et al J Vasc Surg. 2009 Jan;49(1):109-15

In order to establish a sample size, a margin of non-inferiority, delta, was set at 10% for the current study to demonstrate non-inferiority of the PQ Bypass Systems to the historical control in terms of patency. This delta reflects the limited quantitative and qualitative availability of fem-pop bypass studies in the literature. Therefore, a 10% delta is adequate to accurately reflect non-inferiority. This delta sets up a comparison between the lower 95% CI of the PQ Bypass Systems performance to the lower 95% CI reported for the competitive products (~70%).

As such using as historical control rate of 80-85% and a non-inferiority margin of 10%, the null and alternative hypotheses of the primary performance endpoint can be written as:

$$H_0: \pi_{PQB_performance} \leq \pi_{PG_performance}$$

$$H_A: \pi_{PQB_performance} > \pi_{PG_performance}$$

where,

$$\pi_{PG_performance} = 85\% \text{ historical control rate} - 10\% \text{ Delta}$$

$$\pi_{PQB_performance} = \text{PQB Systems success rate}$$

The hypotheses for the primary performance endpoint can be rewritten as:

$$H_0: \pi_{PQB_performance} \leq 70\%$$

$$H_A: \pi_{PQB_performance} > 70\%$$

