- **Q-Wave Myocardial Infarction** – Development of new, pathological Q waves in two or more contiguous leads V1-V3 or Q Wave \geq 3 ms in width in leads I, II, aVL, AVF, V4, V5 or V6 and \geq 1 mm in depth on at least two serial ECGs.
- **Non-Q-Wave Myocardial Infarction** – (1) Non-procedural (pre-procedural or $>$ 30 days post-index procedure, endovascular or surgical intervention) – CK-MB elevation \geq 2 times the upper limit of normal in the absence of new pathological Q waves, (2) post-index procedure or endovascular re-intervention (\leq 30 days) – CK-MB elevation \geq 3 times the upper limit of normal in the absence of new pathological Q waves, or (3) post-Surgical intervention ($<$ 30 days) – CK-MB elevation \geq 5 times the upper limit of normal in the absence of new pathological Q waves.

Post-Procedure ICU Time

Number of hours a patient is in an intensive care unit prior to discharge or moving to a step down or standard care unit.

Primary Assisted Patency

Revascularization of non-occlusive (<99%) stenosis within the stent graft or immediately above or below the treated arterial segment with less than 50% residual stenosis.

Primary Patency

No evidence of clinically significant stenosis (\geq 50%) within the stent graft or immediately above or below the treated arterial segment based on duplex ultrasound (systolic velocity ratio of $>$ 2.5).

Post-Procedure Length of Hospital Stay

Number of days from the end of the procedure until the patient is discharged from the hospital. This does not include time spent in a skilled care facility.

Procedural Success

Successful delivery of the investigational devices to the identified area and removal of delivery system. in the absence of in-hospital MAEs.

Procedure Time

Number of minutes needed to perform the index procedure from time of initial vessel cut down time to time of final guidewire removal. Also referred to as skin-to-skin time.

² Myocardial infarction redefined--a consensus document of The Joint European Society of Cardiology/American College of Cardiology Committee for the redefinition of myocardial infarction. Eur Heart J. 2000 Sep;21(18):1502-13. Review.

Renal Failure

Need for dialysis or a laboratory finding of serum creatinine > 3.5 mg/dL.

Respiratory Failure

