The need for mechanical ventilation beyond the first 24 hours post-index procedure (and/or re-intervention) or the need for re-intubation or ventilator support after the first 24 hours (unless the subject was ventilator dependent pre-procedure).

Secondary intervention

Any visit to the operating room or catheterization laboratory subsequent to the PQ Bypass procedure to treat an adverse event related to the disease, the index procedure or the study device.

Secondary Patency

revascularization of occlusion (100%) within the stent graft or immediately above or below the treated arterial segment with less than 50% residual stenosis

Serious Adverse Event (SAE)

Any undesirable event occurring which led, could have led or might lead either directly or indirectly to the death or serious deterioration in the health of a subject, user or another person, regardless of whether the event was caused by the medical device.

Stroke or Transient Ischemic Attack (TIA)

- **Stroke** - A new neurological deficit lasting more than 24 hours, or lasting 24 hours or less with a brain imaging study showing infarction.
- **TIA** - A neurological deficit lasting less than 24 hours and, if an imaging study is performed, shows no evidence of infarction. These events may occur anytime throughout a subject's study participation and may or may not require intervention.

Stent Graft Occlusion

Complete blockage of blood flow through the Stent Graft as determined by traditional imaging (e.g. DUS, CTA, MRA or Angiography).

Stent Graft Placement Accuracy

Estimated distance (mm) from the operator's intended target as compared to the actual position placed as assessed via angiography during the index procedure.

Target Lesion Revascularization (TLR)

A re-intervention on the index lesion site.

Target Vessel Revascularization (TVR)

Treatment of another lesion at the target vessel site.

Technical Success

Successful delivery of the investigational devices to the identified area and removal of delivery system.

Unanticipated Adverse Device Effect (UADE)

An adverse device effect which by its nature, incidence, severity or outcome has not been identified in the risk analysis report.

Vascular Access Type

Method of entry into the vascular system. Categorized as either surgical cut down or percutaneous.

Venous Classification (Miller Scale)

A means of classifying observations in the deep vein in which the stent graft is implanted:

- 0: Patent, no presence of fibrin or thrombus

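### Primary assisted and secondary patency are defined as re-treatments, so a graft that stays open untouched meets neither, and no Kaplan-Meier failure event is named

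*Combined protocol and SAP*

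**What the plan says.** Both endpoints are worded as a procedure, and the wording is the same in every place.

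- Synopsis, secondary performance endpoints: "Primary assisted patency defined as revascularization of non-occlusive (<99%) stenosis within the stent graft". Section 5.2 repeats this, and section 19 gives it in full: "Revascularization of non-occlusive (<99%) stenosis within the stent graft or immediately above or below the treated arterial segment with less than 50% residual stenosis".
- Section 5.2: "Secondary patency defined as: revascularization of occlusion (100%) within the stent graft". The synopsis repeats this, and section 19 gives it in full: "revascularization of occlusion (100%) within the stent graft or immediately above or below the treated arterial segment with less than 50% residual stenosis".

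None of these places adds that a graft open without re-treatment counts, or that patency must persist after a re-treatment. Primary patency, by contrast, is written in all three places as a state of the graft, namely absence of significant stenosis on duplex.

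On analysis, section 11.1 says: "The secondary endpoint of primary assisted and secondary patency will be summarized using Kaplan-Meier survival analysis". It adds life tables and a curve. It gives no failure event, time origin or censoring rule for these endpoints. Its missing-data paragraph says only that nothing is imputed. Section 19 defines stent graft occlusion but does not link it to either endpoint.

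Section 11.2 reprints life tables from a randomized comparison of stent grafts with prosthetic bypass. Their estimate column is headed "Free from loss of patency", and one of them is "Table V. Secondary patency in femoropopliteal bypass group and stent graft group".

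**The concern.** Assisted and secondary patency are normally read as tiers built on primary patency: each adds rescued grafts to those that never failed, so each is at least as high as the tier below. The written definitions keep only the rescued grafts. An analyst who follows them would report how often a re-treatment succeeded and label it patency. An analyst who does not follow them must choose the event, probably once data are in hand. Follow-up runs to 36 months, so several reports could rest on that choice. In either case the results could not be set beside the comparator tables that the plan itself relies on.

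**Working it through.** The plan states no expected value for either endpoint, so there is no trial figure to reproduce. The check has three parts.

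**1. Apply the definitions to the possible graft histories.** The last two columns show a cumulative-state reading for contrast.

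| Graft history | Assisted, as written | Secondary, as written | Assisted, as a state | Secondary, as a state |
|---|---|---|---|---|
| Open, never re-treated | no | no | yes | yes |
| Non-occlusive stenosis re-treated, residual <50% | yes | no | yes | yes |
| Occluded, re-opened, residual <50% | no | yes | no | yes |
| Occluded, never re-opened | no | no | no | no |

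As written, the best history (first row) and the worst (last row) are classified alike. Counting each graft once, the two written endpoints together equal the share of grafts successfully re-treated. That share is below primary patency whenever fewer grafts are rescued than hold primary patency.

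**2. Use the written event in a Kaplan-Meier analysis.** If successful re-treatment is the event, the rescued grafts in rows two and three are the failures. The occluded graft in row four never has an event and counts with the untouched open graft. The curve would then show freedom from successful re-treatment, with rescue counted as failure.

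**3. Check which concept the comparator tables use.** Inputs are the numbers at risk (n) and events (d) per interval in Table 11-2 of section 11.2. Formula: S = product of (1 − d/n).

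- Stent graft, primary: 48/50 × 42/48 × 40/41 × 36/39 × 34/35 = 0.7349 (printed 0.735).
- Stent graft, secondary: 50/50 × 44/50 × 42/43 × 40/41 × 39/39 = 0.8386 (printed 0.839).
- Bypass, primary: 48/50 × 45/48 × 40/44 × 37/38 × 27/29 = 0.7417 (printed 0.742).
- Bypass, secondary: 48/50 × 46/48 × 42/45 × 39/40 × 31/31 = 0.8372 (printed 0.837).

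All four printed 12-month values reproduce. All 50 limbs per group are at risk from the start, and the curve drops only when patency is lost, so untouched open grafts count as successes. At every printed time point secondary patency is at or above primary; the bypass group at 30 days is the one tie (0.960 for both). The definitions in this plan cannot produce a table of that kind.

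**The case against.** The strongest reply is that the definitions are shorthand for what each tier adds to primary patency. Section 11.2 supports this: it describes the comparator's re-interventions as leading to secondary patency of 83.9% and 83.7%, which is a cumulative use of the term. Section 11.1 also asks for survival analysis and life tables, which suit a state that can be lost. As an account of intent this is plausible, and it stands to that extent. A reader should therefore not infer that the sponsor means to publish re-treatment rates as patency; the documents do not show that. But the shorthand reading contradicts the operative wording in all three places, and no other section supplies the missing clause or the event. It confirms that the text does not match the likely intent.

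A second reply is that section 11.1 calls this a feasibility study reported descriptively, with no target or decision attached to these endpoints. That is correct and limits the weight of the point.

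A smaller question is whether a 99% stenosis falls between the two bracketed limits (<99% and 100%). The word non-occlusive arguably covers it, so this is only a wording repair.

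**Conclusion.** The point holds. The two definitions are wrong as written rather than merely brief, and the Kaplan-Meier plan names no failure event. The primary endpoint and the sample size do not depend on either. The change should be made, but no pass/fail conclusion turns on it.

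The size in this trial cannot be derived, and two stronger readings should be resisted.

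- At the 85% primary patency assumed in section 11.2, a reader might infer that at most 15 of 100 grafts (100 − 85) could meet either written definition. That needs every primary-patent graft to be untouched. The primary endpoint excludes only clinically driven re-treatment of the stented portion, whereas the assisted and secondary definitions also cover the segments just above and below. A graft could therefore hold primary patency and still meet a written re-treatment definition, so 15 is not a strict ceiling.
- A reader might try to size the effect from the comparator's re-intervention counts: "Thirteen patients in the stent graft group had 14 re-interventions, and 12 re-interventions occurred in the surgical group". They come from another device, carry no time window that matches the 12-month patency figures (median monitoring was 18 months), and give no residual stenosis. They do not measure this trial.

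The conclusion rests on reading the definitions literally and on the published text; the case report forms are not available.

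**What to change.** **Definitions (synopsis, section 5.2, section 19).** Write both endpoints as cumulative states.

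- Primary assisted patency: grafts that have never occluded, whether untouched or kept open by re-treatment of a non-occlusive (<100%) stenosis with <50% residual stenosis.
- Secondary patency: the same, plus grafts re-opened after occlusion with <50% residual stenosis.

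**Analysis (section 11.1).**

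- Name loss of the defined state as the Kaplan-Meier event.
- Take occlusion from the section 19 stent graft occlusion entry, extended to the adjacent segments.
- Date an occlusion that is not re-opened at its detection.
- State the time origin and how death, amputation, explant and surgical bypass are handled.
- Choose one rule for non-occlusive stenosis of ≥50%, whether residual after re-treatment or never treated, so that treated and untreated grafts are judged alike. The documents do not settle this rule; the sponsor should fix it before these endpoints are analysed.

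**Minor consistency edit.** The section 19 entry for primary patency omits the re-intervention condition that the synopsis and section 5.2 both include. Align it with them. The primary endpoint itself does not change.

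**Cost.** The work is wording edits, possibly with Ethics Committee and Competent Authority review under section 16.3. The sponsor must also confirm that residual stenosis at re-treatment is captured on the case report forms: the current definitions need it, but the evaluation lists in sections 9.3 to 9.5 do not name it. This matters because section 2.4 reports 60 subjects already treated.

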1.0 PRIMARY CONTACTS

Sponsor and Data Management	PQ Bypass, Inc. [name] [contact] [contact] [name] Vice- President Clinical and Regulatory Affairs PQ Bypass, Inc. [contact] Email: [contact]
Global Monitor / CRO Authorized EU Representative	[name] Quality Manager HealthLink Europe BV HealthLink International Inc. [name] The Netherlands Phone General: [name] [contact] E-mail: [contact] Web:www.healthlinkeurope.com
Legal Representative - Chile	Bioscience Consulting Inc. [name] [name] [contact] Email: [contact]
Core Lab	Vascular Ultrasound Core Lab [name] RN, RVT, FSVU, Technical Director [name] Business Office: [contact] [contact] [contact] [contact] http://vascore.org

PROTOCOL SUMMARY

Title:	PQ Bypass Systems for Femoropopliteal Bypass II (PQB 4 FP II)
Protocol Number	STP 115
Study Design:	Prospective, single-arm, multi-center, international, non-randomized, pre-market, safety and effectiveness clinical investigation evaluating the PQ Bypass Systems to access, deliver guidewires and implant stent grafts for a percutaneous femoropopliteal (fem-pop) bypass.
Study Objective:	To assess the safety and performance of the PQ Bypass System to access, deliver guidewires and implant stent grafts for a percutaneous fem-pop bypass.
Enrollment:	Up to 100 subjects will undergo a percutaneous fem-pop bypass, including up to 30 subjects in Germany.
Number of Sites	Up to 17 international sites (non U.S. sites).
Study Enrollment	24-month enrollment period: 
 • Initial enrollment: Q1, 2015 • Last enrollment: Q1, 2017
Study Duration	60 months (24-month enrollment and 36-month follow-up)
Primary Safety Endpoint:	Major Adverse Events (MAE) at 1 month. MAE is a composite endpoint defined as: 
 • Death • Target Vessel revascularization (TVR) • Target limb amputation

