5.2 Study Endpoints

Primary Safety Endpoint:

Major Adverse Clinical Events (MAE) at 1 month, defined as death, target vessel revascularization (TVR), target limb amputation.

Primary Performance Endpoint:

Primary Patency at 6 month, defined as no evidence of clinically significant stenosis ($\geq 50\%$) within the stent graft or immediately above or below the treated arterial segment based on duplex ultrasound (systolic velocity ratio of >2.5), with no clinically-driven re-intervention within the stented segment.

Secondary Safety Endpoints:

- Major Adverse Events (MAE) through follow-up.
- Major adverse vascular event (MAVE) through follow-up defined as stent thrombosis, target limb amputation, clinically apparent distal embolization, defined as causing end-organ damage (e.g. lower extremity ulceration, tissue necrosis, or gangrene), procedure related arterial rupture, acute limb ischemia or bleeding event requiring transfusion.
- Major Blood Loss defined as transfusion of >2 units packed red blood cells (PRBC) through discharge.
- The combined rate of death of target vessel revascularization (TVR), index limb amputation, and an increase in Rutherford-Becker Classification by 2 classes (comparing pre- to post-procedural assessments) through follow-up.
- Deep Vein Thrombosis (DVT) on ipsilateral limb defined as a symptomatic blood clot (thrombus) in the targeted deep vein (e.g. posterior tibial) through follow-up.
- VCSS and Villalta Scale through follow-up.
- Venous Assessment (Miller Scale) through follow-up.

- Stent fracture identified via X-ray through follow-up. (Optional per standard practice. Not applicable if radiological Safety Committee approval is required e.g. BFS Germany).

Secondary Performance Endpoints:

- Technical Success defined as successful delivery of the investigational devices to the identified area and removal of delivery system.
- Procedural Success defined as successful delivery of the investigational devices to the identified area and removal of delivery system in the absence of in-hospital MAEs.
- Clinical Success defined as Limb ischemia improvement by Rutherford-Becker (improvement in scale by ≥ 1) through follow-up.
- Limb ischemia by Rutherford-Becker Classification through follow-up.
- Primary Patency through follow-up.

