- **Non-device or procedure related death** – Death NOT related to any procedure (index or subsequent) intended to treat the target vessel or death not related to the Study Device.

Deep Vein Thrombosis (DVT) on Ipsilateral Limb

A blood clot (thrombus) in the targeted deep vein (e.g. posterior tibial). A deep vein thrombosis is symptomatic. A deep vein thrombosis is distinct from the presence of mild fibrin/thrombus with no hemodynamic impact or the intentional I occupancy of the vein by the graft or asymptomatic occlusive thrombus (see **Venous Classification** below)

Device Deficiency

Inadequacy of the Study Device with respect to its identity, quality, durability, reliability, safety or performance. Device deficiencies include malfunctions, use errors, and inadequate labeling.

Device Time

Number of minutes from initial Study Device insertion to final Study Device removal. It does not include time needed to perform adjunctive procedures.

Explant

Removal of the Study Device implant for any reason.

Fluoroscopy Time

Total fluoroscopy time (minutes) used during the index procedure and includes time utilized for adjunctive procedures performed during the index procedure.

Intensive Care Unit Time

See post-procedure ICU time

Life Expectancy > 2 Year

The duration of time the test subject is expected survive post procedure. Subjects must not have a concurrent medical condition that would cause expected survival to be less than 2 years.

Malignant Tumor¹

A tumor that invades surrounding tissues, is usually capable of producing metastases, may recur after attempted removal, and is likely to cause death of the host unless adequately treated.

Major Adverse Event (MAE)

¹ <http://www.medilexicon.com>

Composite endpoint of death, target vessel revascularization (TVR) or any amputation of the index limb. See individual events for detailed definitions.

Major Adverse Vascular Event (MAVE)

Composite endpoint of stent thrombosis, target limb amputation, clinically apparent distal embolization, defined as causing end-organ damage (e.g. lower extremity ulceration, tissue necrosis, or gangrene), procedure related arterial rupture, acute limb ischemia or bleeding event requiring transfusion.

Myocardial Infarction (MI)²

Typical chest pain and either a Q-wave or non Q-wave MI as described below. Myocardial infarction is a component of MAE.

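### The primary safety endpoint is MAE at 1 month, but Section 11.1 plans only a 6-month analysis, and Section 19.0 leaves open whether MI and some re-interventions count as MAE

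*Combined protocol and SAP*

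**What the plan says.** **Time point.** The Protocol Summary gives the primary safety endpoint as "Major Adverse Events (MAE) at 1 month", and Section 5.2 agrees. Section 11.1, under Primary Safety Endpoint Reporting, plans the number and percentage of subjects with MAE at 6 months, with a one-sided upper 95% bound by the Score method. It does not mention 1-month MAE.

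**Components.** Section 5.2 has MAE "defined as death, target vessel revascularization (TVR), target limb amputation", and the Protocol Summary lists the same three events. The Section 19.0 entry reads "Composite endpoint of death, target vessel revascularization (TVR) or any amputation of the index limb. See individual events for detailed definitions". In the same section the MI entry states "Myocardial infarction is a component of MAE".

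**TVR.** The individual definition of TVR in Section 19.0 is "Treatment of another lesion at the target vessel site". Target lesion revascularization (TLR) has its own entry, "A re-intervention on the index lesion site", and appears in no primary or secondary endpoint list.

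**The concern.** Two things must be fixed before a primary safety rate can be reported: when it is measured and which events count. Here the analysis section and the endpoint section disagree on the first, and Section 19.0 disagrees with itself on the second.

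The three conflicts do not reach equally far:

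- The time-point conflict affects only the primary safety report.
- The MI conflict affects the MAE-based endpoints: the primary rate, MAE through follow-up, and Procedural Success, which requires no in-hospital MAE.
- The TVR wording affects those three, plus the separate TVR endpoint and the composite that joins TVR, amputation and Rutherford worsening.

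The study is open and single-arm, and Section 2.4 reports 60 subjects already treated by May 2016. If the rules stay unsettled, classification may be decided with outcomes in view.

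**Working it through.** The plan gives no expected MAE rate, safety goal or safety power, so there is no figure to reproduce. The check sets the texts side by side and then sizes the effect.

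**Step 1: what each place says**

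| Place | Time | Components |
|---|---|---|
| Protocol Summary | 1 month | death, TVR, amputation of the target limb |
| Section 5.2 | 1 month | the same three |
| Section 19.0, MAE entry | not given | death, TVR, any index-limb amputation; defers to the individual entries |
| Section 19.0, MI entry | not given | adds MI |
| Section 11.1 | 6 months | not listed |

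**Step 2: how specific events would be classified**

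- *First event between months 1 and 6:* counted under 11.1, not under the stated endpoint.
- *MI:* an MAE by the MI entry, not by any of the three lists.
- *Re-intervention on the index lesion:* TLR by its own entry. Since TVR refers to another lesion, it is not an MAE on a literal reading.
- *Re-intervention on the graft or an anastomosis:* unsettled. Section 2.2 describes the graft leaving the artery above the lesion and re-entering below it. A graft problem could be another lesion (TVR, hence MAE) or fit neither term.

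**Step 3: size per event**

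The Score upper bound named in 11.1, with p = x/n and one-sided z = 1.645 (z² = 2.706), is

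U = [p + z²/(2n) + z·√(p(1−p)/n + z²/(4n²))] / (1 + z²/n).

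Take n = 100, the enrolment ceiling, with assumed counts:

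- x = 0: U = 0.02706 / 1.02706 = 2.63%.
- x = 4: U = (0.04 + 0.01353 + 1.645 × 0.02125) / 1.02706 = 8.62%.
- x = 1, 2, 3: 4.36%, 5.86%, 7.27%.

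Each event moves the rate by 1 point and the bound by 1.35 to 1.73 points. At n = 90 (an assumed shortfall; 11.1 plans no imputation, and 11.2 expects no loss) the bounds for 0 and 4 events are 2.9% and 9.5%. At n = 60 they are 4.3% and 14.0%.

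For Procedural Success at n = 100, with the 95% bounds taken as two-sided (z = 1.960, an assumption), re-classifying one in-hospital event moves the rate from 100% to 99%. The lower bound moves from 96.30% to 94.55%.

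**Step 4: the time point**

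The documents give no MAE counts by month. The nearest figure is the primary patency table from the randomized study cited in Section 11.2. In its stent-graft arm of 50 limbs, cumulative losses of patency rise from 2 by day 30 to 9 by day 227. Crude rates are 2/50 = 4% and 9/50 = 18%, with Score upper bounds of 11.4% and 28.5%. These are patency losses in another study, not MAEs. They show only that a 1-month and a 6-month count can differ considerably.

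**The case against.** The strongest defence is that little turns on this. Safety is descriptive and has no performance goal, so no test can pass or fail because of it. That stands, and it limits the effect to reported rates and bounds.

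Nor are the events lost. Section 12.0 records all adverse events, and primary patency in Section 5.2 requires an outcome "with no clinically-driven re-intervention within the stented segment". That also stands, but recording an event does not decide whether it belongs in the composite.

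A reader might infer that the protocol removes device-related re-intervention from the safety endpoint. The documents do not support that. The literal exclusion covers only the index lesion, which this procedure bypasses, so re-intervention there may be uncommon. For the graft and anastomoses the wording is unclear and can be read as counting them. Conversely, a reader may suppose that TVR was meant to include TLR, but no text says so, and the MAE entry sends the reader to the individual definitions.

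The revision log mentions an Appendix III justifying the endpoints. It was not among the material available and could bear on the scope of TVR. It would not remove the contradictions within Section 19.0 or between 5.2 and 11.1.

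**Conclusion.** The point holds and should be fixed. The time-point conflict is the clearest defect: followed as written, 11.1 reports the primary safety result at 6 months and leaves the stated 1-month endpoint unanalysed. The MI conflict is equally plain in the text. The TVR definition needs clarifying; confidence is lower there, because only index-lesion re-intervention is literally left out.

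The effect is about 1 percentage point in the MAE rate per event at 100 subjects, with the upper bound running from 2.6% (0 events) to 8.6% (4 events). Those counts are assumed.

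Two stronger readings should be resisted. It does not follow that all three conflicts disturb all five endpoints; only the TVR wording does. Nor is the direction of bias known: a wider TVR would raise the MAE rate, leaving MI out would lower it if MI had been counted, and graft re-intervention could go either way.

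Two differences are matters of harmonisation only: the amputation wording, and the Section 19.0 Primary Patency entry, which describes stenosis "within the stent graft or immediately above or below the treated arterial segment based on duplex ultrasound" but omits the re-intervention clause found in 5.2.

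**What to change.** 1. In Section 11.1, report 1-month MAE with the Score upper bound as the primary safety result. Keep 6-month MAE under the secondary endpoint of MAE through follow-up.
2. Use one MAE component list in the Protocol Summary, 5.2 and 19.0. The sponsor should state whether MI counts and report MAE with and without it.
3. State in the TVR definition that it covers re-intervention on the index lesion, the stent grafts and the anastomoses, with TLR as a subset. This scope is a proposal; the documents do not fix it.
4. Label the change as made after enrolment began. State how such events were classified until then, and tabulate MAE, TVR and Procedural Success under both readings. The revision log places an update of the primary safety endpoint and the addition of the definitions at revision E, so the wording in force for earlier subjects should be stated.
5. Harmonise the amputation wording and the Primary Patency entry in the same edit.

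The cost is an amendment handled under Section 16.3, re-classification of events already collected and a second tabulation; no new visits or tests. The definition is revised with outcomes partly known, and the MAE rate may rise (wider TVR) or fall (if MI is excluded), which is why both readings must be shown.
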